1.2.1.2 Proteomic dataset (Luminex)

A Bio-Plex Pro Assay kit was utilised to assess the concentrations of cytokines, chemokines and growth factors in the study population from samples taken on days 1 (pre-treatment), 5 and 10 of admission. The 27 cytokines, chemokines and growth factors measured are: IL-1 β , IL-1ra, IL-2, IL-4, IL-5, IL-6, IL-7, CXCL8/IL-8, IL-9, IL-10, IL-12p70, IL-13, IL-15, IL-17A, Eotaxin, Basic FGF, G-CSF, GM-CSF, IFN- γ , IP-10, CCL2/MCP1, CCL3/MIP-1 α , CCL4/MIP-1 β , PDGF-BB, CCL5/RANTES, TNF- α and VEGF. Following analysis of each batch, 27 reports (one for each analyte) containing the assay results (in pg/ml) were generated using the xPONENT for MagPix software and saved within the study specific electronic file. A CSV file will be generated and exported for further analysis.

1.2.1.3 SARS-CoV-2 viral load dataset

RNA was extracted using the QIAmp viral RNA mini kit (Qiagen). PCR for SARS-CoV2 targets was performed using the CE-marked COVID-19 genesig Real-Time PCR assay (Primerdesign).

1.2.1.4 SARS CoV-2 serology dataset

Anti-SARS-CoV2 IgG antibodies in serum were measured using the Elecsys Anti-SARS-CoV-2 nucleoprotein assay (Roche)(2)

1.2.1.5 Pharmacokinetic drug concentration dataset

A pharmacokinetic dataset is available for each subject who received at least 1 dose of experimental drug and in whom drug levels were detectable. PK assessments were specific to the candidate agent and delivered by the pharmaceutical partners using validated assays for drug registration.

1.2.1.6 Clinical Laboratory variables dataset

Standard clinical laboratory safety testing was performed on all subjects, including haematology, coagulation and clinical chemistry readouts which are available for analysis of response.

2 Analysis plan

2.1 Missing data, interpolation, and imputation

Missing data will be minimised, with outcomes collected after premature withdrawal of treatment. The primary clinical estimate will be analysed using a treatment policy strategy. If an OSS is missing on a particular study day, the unscheduled visits will be considered to see whether there was an unscheduled visit on that day. If so, the score from the unscheduled visit will be used. For the purposes of the primary analysis patients who died or were transferred will not be censored at day of death/transfer, time to clinical response will instead be censored as 29 days. Patients are considered to be in the study until Day 29 but a score of 8 will be imputed for the OSS for those who died from their date of death and for all subsequent visits. Moreover, if a patient withdraws and then dies and we have a record of their death then a score of 8 will be imputed from their date of death onwards for all analyses. For those who transferred, additional data post transfer has been collected and will be used. If a patient is discharged, has no Day 29 value but has a day 60 value they will be considered Alive for the mortality analysis and Last observation carried forward (LOCF) will be used to impute Day 29. If a patient has discharged and no additional data are available, then they are assumed alive at Day 29 and LOCF will be used to impute Day 29 value. If the OSS is missing on the date of discharge, this will be imputed to 2 (most conservative value possible for discharged patients). If the OSS is \geq 3 on the date of discharge, then the score will be imputed to 2. If a patient is subsequently readmitted and has ordinal scale data, then this data will be used. However, if data has not been entered upon readmission, then the patient will be considered a non-responder for the primary endpoint. Once they have been discharged then if OSS is missing it will be imputed as 2 for subsequent days. Reported ethnicity will be compared with ancestral ethnicity inferred using genetics data (Peddy software) and mapping of genotypes to gnomAD v2.1.1 data. Inferred (genetic ancestry) will be preferred over reported ancestry where discrepancies occur. Sex will be calculated counting genotypes on the X chromosome and be used preferentially where gender may not match biological sex.

2.2 Comparison and confounding of baseline clinical characteristics

Baseline clinical characteristics, including age, sex, ethnicity, significant comorbidities, laboratory results and clinical observations will be recorded, assessed and compared between patients in different treatment arms using R (v 4.1.2). Patient statistics tables will be calculated to test for any significant confounding variables between blinded groups. Principal component analysis of normalised expression values will be correlated with axes of variation e.g. ethnicity, to identify clusters affecting gene expression.

Differential gene expression analysis will control for baseline factors that may skew analysis by updating the statistic model design in DESeq2. Differential splicing analysis will be subject to weighting by multinomial covariate-balanced propensity scores to control for baseline confounding factors, as implemented by the R package Weightlt version 0.12.0, using the "just-identified" approach. Proteomics models will incorporate weighted baseline clinical data to avoid bias.

2.3 Transcriptomic analysis

The focus of this study will be the analysis of the transcriptomics dataset comprising patient data taken at three time points for three novel drugs and the SoC trial arm. The RNA-Sequencing samples have been generated and the raw FASTQC data have been downloaded from the ACCORD clinical trials platform. These data have been subject to quality control as previously described in the methods section. To avoid any unintentional bias, the groups will be blinded so that the bioinformatician will not know which patient group or SoC arm is which. The novel drug and SoC arms will be given a random identifier such as A, B, C or D for the duration of this analysis.

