1.1 Study Population

The inclusion criteria for the ACCORD trial were:

Adults (>= 18 years) with SARS-CoV-2 infection confirmed by laboratory tests and/or point of care tests. Patients must be scored between Grade 3 (hospitalised – mild disease, no oxygen therapy) to Grade 5 (hospitalised - severe disease, non-invasive ventilation or high flow oxygen) on ACCORD's 9 point WHO ordinal scale from clinical improvement (OSCI) where Grade 0 is uninfected and 8 is death. Overall, in the ACCORD study 167 subjects were randomised, 14 subjects withdrew and 25 subjects died. In the additional Bemcentinib study, a further 115 were randomised – 60 to SoC and 55 to Bemcentinib in an identical study design.

1.2 Sampling.

Samples from patients were collected in line with the sample collection schedule below:

	Baseline								
Day	1	3	4	5	8	10	11	15	29
Biological sample type									
Blood (for RNA)	Х			Х		Х			
Blood (for serology)	Х							Х	
Blood (for protein)	Х			Х		Х			
Oropharyngeal swab (for viral load)	Х	Х		Х	Х		Х	Х	Х
Pharmacokinetic drug concentration									
Bemcentinib	Х		Xa		Х			Х	
Tozorakimab	Xb							Xc	
Zilucoplan	Х			Х		Х		Х	

Table showing the sample collection schedule for the ACCORD COVID-19 clinical trial.

Adapted from (1) to show only the samples collected to generate the datasets relevant to this current project. X = sample collected. All patients were sampled on day 1, which is considered baseline prior to the first dose of the assigned treatment arm or standard of care. Each drug had slightly different pharmacokinetic (PK) sampling regimes and were mostly collected predose. Where samples for PK were collected other than pre-dose, collection information is detailed below:

- ^a Sample collected pre-dose and 6 hours post-dose (Day 4).
- ^b Sample collected pre-dose and 15 minutes post-dose (Day 1).
- ^c Sample collected pre-dose and 15 minutes post-dose (Day 15).

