2.5 Other Factors

Viral Load, SARS-CoV-2 Serology, Pharmacokinetic drug concentration, patient demographics and clinical severity (baseline OSCI score) will be included in the pathway analysis model. These factors will be coded as numerical values and input as clinical traits for analysis of correlation with eigengene values of gene cluster modules within the WGCNA work stream.

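### Background medication started after Day 1 is outside every control the omics models state, and Day 1 medication is not named, so the non-randomised contrasts may credit co-medication effects to the study drug

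*Protocol*

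**What the plan says.** **What is controlled.** Section 2.2 lists what is compared across arms: "Baseline clinical characteristics, including age, sex, ethnicity, significant comorbidities, laboratory results and clinical observations will be recorded, assessed and compared". It then gives a rule for each type of data:

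- Expression: "Differential gene expression analysis will control for baseline factors that may skew analysis by updating the statistic model design in DESeq2".
- Splicing: "Differential splicing analysis will be subject to weighting by multinomial covariate-balanced propensity scores to control for baseline confounding factors".
- Protein: "Proteomics models will incorporate weighted baseline clinical data to avoid bias".

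Section 2.3.1 repeats that the DESeq2 design handles baseline characteristics. Section 2.5 adds: "Viral Load, SARS-CoV-2 Serology, Pharmacokinetic drug concentration, patient demographics and clinical severity (baseline OSCI score) will be included in the pathway analysis model". These enter as traits correlated with module eigengenes in the WGCNA work.

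**Which contrasts are run.** Section 2.3.1 starts with pre- versus post-treatment expression within each drug arm, to find the pathways behind drug response. It goes on to responder signatures within each drug, and then to each drug against SoC. Section 2.3.4 repeats the pre/post and drug-versus-SoC comparisons for splicing. Section 2.4 compares the 27 proteins by drug versus SoC and by response within arm.

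**What Day 1 means.** Section 1.2 describes the Day 1 sample as one "which is considered baseline prior to the first dose of the assigned treatment arm or standard of care". Section 1.1 admits only patients already in hospital, up to Grade 5: "hospitalised - severe disease, non-invasive ventilation or high flow oxygen".

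No section mentions steroids, other immunomodulators, antivirals, or concomitant or rescue medication. SoC is not defined.

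**The concern.** Blood RNA and circulating cytokines are readouts on which anti-inflammatory co-medication can be expected to act directly. If some patients start such a drug between Day 1 and Day 5 or 10, its footprint is in the later samples. A within-arm pre/post contrast has no concurrent control and counts that footprint as drug response. A responder contrast is not randomised. If patients who do badly are given more background medication, part of the signature shows who was treated with what.

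Control by baseline factors does not reach this. A factor fixed at baseline has the same value in a patient's Day 1 and Day 5 samples, so as a main effect it cannot account for a change between them.

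At stake is what the project is meant to deliver: mechanisms of action and endotypes of response. A pathway moved by background treatment could be reported as either.

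**Working it through.** **Check of the text.**

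| Place | Factors stated | Medication other than study drug? |
|---|---|---|
| 2.2, comparison of arms | age, sex, ethnicity, comorbidities, laboratory results, observations (open list) | not named |
| 2.2 and 2.3.1, expression | baseline factors, unspecified | not named; later starts not covered |
| 2.2, splicing | baseline confounders, by weighting | not named; later starts not covered |
| 2.2, protein | weighted baseline clinical data | not named; later starts not covered |
| 2.5, pathway traits | viral load, serology, drug levels, demographics, baseline severity score | no |

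Day 1 medication is therefore unnamed, and medication started later is outside all five.

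**Illustration of size.** The protocol gives no figure to reproduce and no usage or effect data. Except for the arm sizes of 55 and 60, every input below is an assumption.

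*Within-arm pre/post, inert study drug.* Let s be the effect of the background drug on a responsive gene, in SD of the paired change, and f the share of patients starting it after Day 1. The spurious mean change is s × f. With s = 0.5 to 1.0 and f = 10% to 50%, it runs from 0.5 × 0.10 = 0.05 SD to 1.0 × 0.50 = 0.50 SD. For a nominal two-sided 5% paired test on one gene, by normal approximation, P(reject) = 1 − Φ(1.96 − b√n) + Φ(−1.96 − b√n), where b is the spurious change:

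| b (SD) | n = 20 pairs | n = 50 pairs |
|---|---|---|
| 0.05 | 6% | 6% |
| 0.15 | 10% | 19% |
| 0.30 | 27% | 56% |
| 0.50 | 61% | 94% |

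*Responder versus non-responder.* The bias is s × (difference in use). A gap of 10 to 30 points gives 0.5 × 0.10 = 0.05 to 1.0 × 0.30 = 0.30 SD. On the log2 scale, take an effect of 1 unit and use of 80% versus 50%: the false signature is 1 × 0.30 = 0.30. With SD 0.7 and 20 per group, z = 0.30 / (0.7 × √(2/20)) = 1.36. Effects of 0.5 and 2 log2 units give z = 0.68 and 2.71.

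*Drug versus SoC, medication before randomisation.* The expected bias is 0. Chance imbalance has SE √(p(1−p)(1/55 + 1/60)), using the one pair of arm sizes in section 1.1. At p = 50% the SE is 0.093, so the 95% range is ±18 points; at p = 20% or 80% it is ±15 points. For s = 0.5 to 1.0, ±18 points is ±0.09 to ±0.18 SD, which ordinary standard errors already cover.

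*Drug versus SoC, medication after Day 1.* If 30% of SoC and 10% of drug patients start a drug worth 1 log2 unit, the arms differ by 1 × 0.20 = 0.20. With SD 0.7 and 20 per group, z = 0.20 / (0.7 × √(2/20)) = 0.90 (0.45 to 1.81 for effects of 0.5 to 2).

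**The case against.** Several points on the other side are sound.

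- **The list is open.** The sentence in 2.2 gives examples, and the DESeq2 rule covers any baseline factor that may distort the analysis. A reader might infer that Day 1 medication is excluded. The text does not say so, and a full covariate list may sit in an analysis plan that is not shown. Its absence from the dataset list in 1.2.1 proves little, since that list covers assays on samples and omits age and comorbidities too. This answers the Day 1 part, but not medication started later, because the stated rules stop at baseline.
- **Day 1 is not shown to be wrong.** A reader might infer from the Grade 5 criterion that Day 1 samples mix patients on and off immunomodulators. Respiratory support shows that care had begun; it does not show that any such drug had been given. The wording can also be read as before the first dose under the allocated arm. What stands is that section 1.2 itself speaks of a first dose of SoC, never defines it, and sits uneasily beside a population already in hospital.
- **Drug versus SoC is different.** Randomisation balances earlier medication in expectation. If later starts differ because the drug works, the difference is a consequence of treatment and part of its total effect, so calling it simply a false effect goes too far. Whether it counts as mechanism is a matter of interpretation.
- **The numbers are assumed.** Many of the illustrative shifts would not reach nominal significance for one gene, before any multiplicity correction. Genes in one pathway would shift together, but that has not been quantified.

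**Conclusion.** The point holds in limited form. The stated controls do not reach background medication started after Day 1, and they do not name Day 1 medication. The pre/post contrasts (2.3.1, 2.3.4) and responder contrasts (2.3.1, 2.4) are not randomised and may therefore credit co-medication to the study drug. The pre/post contrast would also lack a concurrent control even if medication were fully adjusted for.

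The size cannot be known from the protocol. The range of 0.05 to 0.50 SD for pre/post and 0.05 to 0.30 SD for responder contrasts rests wholly on assumed effects and usage. A reader might conclude that steroid effects will be reported as mechanism throughout. The protocol does not support that: it does not show that such drugs were used, and drug versus SoC is protected in expectation against medication given before randomisation. This is a change worth making because it is cheap and bears on the main claims. It is not a demonstrated bias.

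**What to change.** 1. If the parent trial recorded concomitant medication, link start and stop dates to each sample.
2. Name Day 1 use of systemic corticosteroid, other immunomodulator and antiviral as covariates in the DESeq2 design, the splicing weights and the protein models, and add them to the traits in 2.5.
3. Flag Day 5 and Day 10 samples taken after a new start of such a drug. Repeat the drug-versus-SoC and responder contrasts without them as a supportive sensitivity analysis. Do not make persistence a condition for a mechanism claim: removal conditions on an event after randomisation, may select patients differently by arm, and loses power. For the same reason, do not simply add later medication as a covariate.
4. Rest mechanism claims on the change from Day 1 compared with SoC, and label the pre/post and responder contrasts as descriptive.
5. State in 1.2 whether Day 1 precedes only the first study dose or also any SoC drug, and reconcile this with the entry criteria in 1.1.

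Cost: one data link, a few degrees of freedom, one extra run on fewer samples and some rewording. Steps 1 to 3 depend on medication records that the protocol does not mention; steps 4 and 5 do not.

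### Section 2.2 looks for covariates by testing baseline differences between arms for significance; for the randomised drug v SoC contrasts this is a poor selector that costs power, though it does not inflate overall type I error

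*Protocol*

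**What the plan says.** Section 2.2 opens with an open-ended list: "Baseline clinical characteristics, including age, sex, ethnicity, significant comorbidities, laboratory results and clinical observations will be recorded", to be compared between treatment arms. It then states the purpose of the comparison: "Patient statistics tables will be calculated to test for any significant confounding variables between blinded groups". A second data-driven step follows: "Principal component analysis of normalised expression values will be correlated with axes of variation e.g. ethnicity, to identify clusters affecting gene expression".

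The consequence for the gene-expression model comes next: "Differential gene expression analysis will control for baseline factors that may skew analysis by updating the statistic model design in DESeq2". Section 2.3.1 repeats, without naming variables, that baseline characteristics will be controlled for in the DESeq2 design. For splicing the route is different: "Differential splicing analysis will be subject to weighting by multinomial covariate-balanced propensity scores to control for baseline confounding factors". Proteomics models are to use weighted baseline clinical data, but section 2.4 expects to use Mann-Whitney tests.

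Baseline OSCI grade is not named in section 2.2. Section 2.5 names it among the factors for the pathway model and as a trait to correlate with WGCNA modules. Section 1.1 confirms that the arms were formed by randomisation: "in the ACCORD study 167 subjects were randomised", with a further 115 (60 SoC, 55 Bemcentinib) in the additional study. Nowhere does the protocol commit to known prognostic factors whatever the baseline tests show.

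**The concern.** In a drug v SoC contrast between randomised arms, a baseline p-value asks whether chance could have produced a difference that, under proper randomisation, chance did produce. How far a covariate distorts or blurs a contrast depends on two things: the size of the imbalance and the covariate's link with expression. A between-arm p-value does not measure the link, and in small arms it responds only to large imbalances.

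A rule that adjusts only for flagged variables therefore leaves moderate prognostic imbalances in the estimate. It also gives up the precision of known predictors whenever the arms happen to be balanced, which is most of the time. Section 2.6 itself stresses that the data are few and noisy, so lost precision is expensive here. Severity is the obvious example of a predictor at risk: eligible patients ran from OSCI grade 3 (no oxygen) to grade 5 (non-invasive ventilation or high-flow oxygen).

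**Working it through.** The protocol gives no power, alpha or per-arm RNA count, so there is no design figure to reproduce. Its own counts agree: 60 + 55 = 115 and 286 − 14 = 272.

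**Inputs.**
- 60 v 55: the randomised numbers in the additional Bemcentinib study (section 1.1). The protocol does not say whether those patients contribute RNA samples.
- 23 v 23: the 272 usable RNA samples (section 1.2.1.1) over 3 days and 4 arms, 272/12 = 22.7. An even spread is an assumption.
- Two-sided alpha 0.05, covariate–outcome correlation r of 0.3, 0.5 or 0.7, and 6 to 30 baseline variables: all assumptions.

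**1. What the screen can see.** The standard error of a standardised difference is √(1/n₁ + 1/n₂): 0.187 for 60 v 55 and 0.295 for 23 v 23. The smallest significant observed difference is 1.96 times this: 0.37 SD and 0.58 SD. The probability of flagging an underlying difference d is about Φ(d/SE − 1.96):

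| Difference | 60 v 55 | 23 v 23 |
|---|---|---|
| 0.3 SD | 36% | 17% |
| 0.5 SD | 76% | 40% |
| 30% v 45% comorbidity | 38% | 18% |

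Under randomisation the underlying difference is zero and what matters is the observed one, so this was also simulated (40,000 runs, one normal covariate, two arms). An observed imbalance of at least 0.3 SD arose in about 11% (60 v 55) or 31% (23 v 23) of runs and went unflagged in about 54% or 84% of those.

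**2. Conditional error.** In the runs with an unflagged imbalance of at least 0.3 SD, at r = 0.5, the unadjusted test rejected a true null in 10.8% (60 v 55) or 7.4% (23 v 23).

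**3. Overall error and power.** Same simulation, three strategies. The power columns are for a 0.5 SD effect at r = 0.5; the type I error ranges cover both sizes and all three correlations.

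| Strategy | Type I error | Power, 60 v 55 | Power, 23 v 23 |
|---|---|---|---|
| Never adjust | 0.049–0.051 | 0.76 | 0.39 |
| Adjust only if baseline p < 0.05 | 0.036–0.049 | 0.77 | 0.38 |
| Always adjust | 0.048–0.052 | 0.86 | 0.48 |

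The screen performs about as if there were no adjustment. Always adjusting at r = 0.5 leaves a residual variance of 1 − 0.25 = 0.75, and 1/0.75 = 1.33, equivalent to 33% more patients.

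**4. Chance flags.** With k independent null tests the probability of at least one flag is 1 − 0.95^k: 26% (k = 6), 40% (10), 64% (20), 79% (30). Adjusting for a chance imbalance does not bias the contrast; the figure shows only that the covariate set would depend on the sample.

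**The case against.** Several objections are sound and limit the point.

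- **The link from test to model is inferred.** Section 2.2 never says that only significant variables enter the design, and section 2.3.1 promises control for baseline characteristics without condition. A reader might infer a strict p < 0.05 entry rule; the text does not state one. What it does state is a test followed by an update of the model.
- **There is a second selector.** The principal-component correlation does look at expression, so the procedure does not ignore that link. It is still chosen from the data and commits to no covariate.
- **Not every analysis is screened.** No p-value screen is stated for splicing or proteomics. The splicing weights have a different weakness: their inputs are described only as baseline confounding factors.
- **Baseline tests are not always tests of chance alone.** Responder v non-responder contrasts are not randomised, pooling two separately randomised studies can create real differences between arms, and patients with usable samples may be a selected subset. Tests between arms would not find the confounders of a responder contrast either.
- **Baseline OSCI is not excluded.** The section 2.2 list is illustrative and includes clinical observations, and section 2.5 uses OSCI in the pathway work. Reading section 2.2 as leaving severity out goes too far.
- **The error rate can be overstated.** At an assumed 30 or 40 per arm, an unflagged 0.4 SD imbalance with r of 0.5 to 0.7 gives a conditional error of 9–11% or 11–16%. But an unflagged imbalance that large occurs only about 7% or 2.4% of the time per covariate, and at zero imbalance the same formula gives about 2.4% (r = 0.5) or 0.6% (r = 0.7).

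A full covariate list may sit in an analysis plan not shown here, and its absence is not the complaint. The complaint is the selection method that the protocol does state.

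**Conclusion.** The point stands for the between-arm DESeq2 models in the randomised drug v SoC contrasts. Testing baseline differences for significance is a poor way to choose covariates: on the assumed sizes it flags a 0.3 SD difference about 17–36% of the time and gives up about 0.10 of power for a 0.5 SD effect at r = 0.5.

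A reader might infer that false positives rise overall. They do not: the two-step rule is, if anything, slightly conservative. The harm is lost power, together with bias in those samples where a prognostic imbalance goes unflagged.

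The sizes rest on assumed arm numbers, correlations and a 0.05 level, and on a single normally distributed covariate and outcome rather than DESeq2's count model. The direction does not depend on them, provided that the covariate is prognostic. The change is worth making, but the work is mechanistic and the wording leaves some room, so it is a recommended correction, not a fatal flaw.

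**What to change.** Keep the baseline tables as description, with standardised differences, and drop their use as a test. Fix in advance one prognostic set for the between-arm DESeq2 models and the limma models of GSVA scores, and as inputs to the splicing weights: age, sex, baseline OSCI grade and, if samples from the additional Bemcentinib study are used, study. Use it whatever the baseline tables show.

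- **Day 1 expression.** DESeq2 fits one design to all genes, so handle this through an arm-by-day term, not a gene-specific covariate.
- **Proteins.** A Mann-Whitney test takes no covariates. Replace it for the drug v SoC contrasts with a regression on log or rank-transformed values, adjusted for the Day 1 level and the same set.
- **Sequencing lane.** Include it only if it is recorded and not confounded with arm or day; the protocol shows neither.

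The cost is a few degrees of freedom and a changed protein method, so it is more than an edit of wording. Age, sex and clinical observations are already recorded under section 2.2, and baseline OSCI is already used in section 2.5. Whether study is needed depends on which patients supplied samples, which the protocol should state.
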